# 4.6. Study Procedures

After the screening period, subjects will return to the clinic at Baseline and 4, 8 and 12 weeks of the open-label stabilization period. Subjects will have a telephone visit at Week 2 to assess adverse events (AEs) and other safety parameters. Efficacy assessments will be conducted at Weeks 4, 8 and 12. Safety assessments will be conducted at all visits. During the R/WD period, subjects will return to the clinic every week for the first 4 weeks and every 2 weeks thereafter (Weeks 13, 14, 15, 16, 18, 20, 22 and 24) and efficacy and safety assessments will be conducted at each of these visits.

A Follow Up visit will be conducted in the clinic 7 and 14 days after the last dose of study medication. Subjects will also be contacted 30 days after the last dose of study medication to determine any adverse events. At study completion or early termination, subjects will be tapered off study drug as outlined in the protocol. See Table 3 from the protocol for the Schedule of Assessments.

# 5. Endpoints

# 5.1. Primary Efficacy Endpoint

Time from Randomization (Week 12) to Relapse in subjects between the ages of ≥ 6 and <18
years for ecopipam compared to those receiving placebo during the double-blind, R/WD period.

### 5.2. Secondary Efficacy Endpoint

 Time from Randomization (Week 12) to Relapse in all subjects irrespective of age for ecopipam compared to those receiving placebo during the double-blind, R/WD period.

# 5.3. Exploratory Endpoints

- 1. Time from Randomization (Week 12) to a worsening by at least one category of the Global Impression Tourette's Syndrome of Severity (CGI-TS-S) in subjects ≥ 6 and < 18 years for ecopipam compared to those receiving placebo during the double-blind, R/WD period. If there is a strong correlation of this endpoint with Relapse criteria based on the YGTSS-TTS, it may be considered as a secondary endpoint with agreement from Health Authorities.
- 2. Time from Randomization (Week 12) to a worsening by at least one category of the CGI-TS-S in all subjects for ecopipam compared to those receiving placebo irrespective of age. If there is a strong correlation of this endpoint with Relapse criteria based on the YGTSS-TTS, it may be considered as a secondary endpoint with agreement from Health Authorities.
- 3. Mean change from Randomization (Week 12) to Week 24 in the YGTSS-TTS for ecopipam compared to placebo.
- 4. Mean change from Randomization (Week 12) to Week 24 in the CGI-TS-S for ecopipam compared to placebo.
- 5. Mean change from Randomization (Week 12) to Week 24 in the YGTSS-Global Severity (GS) Score for ecopipam compared to placebo.
- 6. Mean change from Randomization (Week 12) to Week 24 in the Caregiver Global Impression of Change (CaGI-C) for ecopipam compared to placebo.
- Time from Randomization (Week 12) to a loss of ≥ 50% of the improvement from Baseline (Day 1) experienced on the YGTSS-TTS at the last visit (Week 12) in the open-label Stabilization period.
- 8. Mean change from Randomization (Week 12) to Week 24 in the Clinical Global Impression of Tourette Syndrome Improvement (CGI-TS-I) for ecopipam compared to placebo.
- 9. Mean change from Randomization (Week 12) to Week 24 in the Premonitory Urge for Tics Scale (PUTS) for ecopipam compared to placebo.
- Mean change from Baseline (Day 1) to Week 24 in Gilles de la Tourette Syndrome

  —Quality of
  Life Scale for Children and Adolescents (C&A-GTS-QOL) score for ecopipam compared to
  placebo.
- 11. Mean change from Baseline (Day 1) to Week 24 in Gilles de la Tourette Syndrome–Quality of Life Scale (GTS-QOL) score in adults for ecopipam compared to placebo.

This document is confidential.

SAP text Version: SAP text 3.0 6-Dec-2023

Controlled Document ID: 3903A.02, Effective Date 31-Aug-2020

- 12. Mean change from Baseline (Day 1) to Week 12 in the YGTSS-TTS.
- 13. Percentage of subjects with a decrease in their YGTSS-TTS by 25% or greater at any time point from Baseline (Day 1) to Week 12.
- 14. Mean change from Baseline (Day 1) to Week 24 in the YGTSS-TTS for ecopipam compared to placebo.
- 15. Mean change from Baseline (Day 1) to Week 24 in the YGTSS-GS score for ecopipam compared to placebo.
- 16. Mean change from Baseline (Day 1) to Week 24 in the Clinical Global Impression of Tourette Syndrome Severity (CGI-TS-S) for ecopipam compared to placebo.
- 17. Caregiver Global Impression of Change (CaGI-C) through Week 24 for ecopipam compared to placebo.
- 18. Mean change from Randomization (Week 12) to Week 24 in the Gilles de la Tourette Syndrome–Quality of Life Scale for Children and Adolescents (C&A-GTS-QOL) for ecopipam compared to placebo.
- 19. Clinical Global Impression of Tourette Syndrome Improvement (CGI-TS-I) through Week 24 for ecopipam compared to placebo.
- 20. Time from Randomization (Week 12) to treatment discontinuation during the double-blind R/WD period for ecopipam compared to placebo.
- 21. Time from Randomization (Week 12) to loss of ≥ 100% of the improvement experienced on the YGTSS-TTS from Baseline (Day 1) to the last visit (Week 12) in the open-label Stabilization period for ecopipam compared to placebo.
- 22. To evaluate the population PK/pharmacodynamic (PD) relationships with ecopipam during the open-label Stabilization period of the study.
- 23. Mean change from Randomization (Week 12) to Week 24 in the YGTSS subscales (Motor, Vocal, and Impairment) for ecopipam compared to placebo.
- 24. Mean change from Baseline (Day 1) to Week 24 in the YGTSS subscales (Motor, Vocal, and Impairment) for ecopipam compared to placebo.

# 6. Analysis Sets

#### 6.1. Screened Set

The Screened Set will include all subjects screened. Unless specified otherwise, this set will be used for subject listings and for summaries of subject disposition.

# 6.2. Safety Set

The Safety Set (SS) will include all enrolled subjects who received at least one dose of study drug. The SS will be used for the analysis of the safety endpoints.

# 6.3. Modified Intent-to-Treat (Primary Efficacy Analysis Set)

The Modified Intention-to-Treat (mITT) set will include all randomized subjects who received at least one dose of study drug post randomization. The mITT set will be used for the analysis of primary, secondary and exploratory efficacy endpoints. Subjects will be analyzed according to randomized treatment.

#### 6.4. Intention-to-Treat Set

The Intention -to -Treat Set (ITT) will include all randomized subjects. While the mITT will be the primary population for efficacy analysis, regulatory authorities may require or prefer an analysis based on the ITT population. All analyses performed for the mITT population will also be performed for the Intent-to-Treat population. Subjects will be analyzed according to randomized treatment.

#### 6.5. Per Protocol Set

The Per-Protocol (PP) set will include subjects from mITT set who have no major protocol deviations that may adversely impact assessment of efficacy. Before data are released for statistical analysis, a blinded review of all data will be performed by the Sponsor's clinical team to identify protocol deviations that may potentially affect the results. At this time, it will be determined whether subjects and/or data should be excluded from the PP set. The list of subjects or observations to be excluded from the PP set, along with the reason for exclusion, will be finalized prior to database unblinding. Protocol deviations that occur due to COVID-19 related issues or other qualifying events will be categorized separately as applicable.

#### 6.6. Pharmacokinetic Set

The Pharmacokinetic Set (PKS) will include all subjects who received at least one dose of the study drug and have at least one valid PK concentration measured.

PK concentrations will be listed for all subjects in the PK set.

### 6.7. Protocol Deviations

Protocol deviations will be collected and categorized as shown in the protocol deviation and non-compliance management plan.

# 7. Estimands

# 7.1. Primary Efficacy Estimand

The primary estimand is defined as the following:

Treatment: 4-week titration period followed by 8-week maintenance during open label stabilization period and 12 weeks of double blinded withdrawal period with ecopipam HCl doses or matching placebo.

Population: Children and adolescent patients with Tourette's syndrome.

Primary Endpoint: Time from Randomization (Week 12) to Relapse (defined as loss of  $\geq$  50% of the improvement experienced on the YGTSS-TTS from Baseline (Day 1) to the last visit in the open-label Stabilization period (Week 12), or initiation of additional medications to treat symptoms of TD, or requirement of hospitalization for worsening symptoms of TD) in subjects between the ages of  $\geq$  6 and <18 years for ecopipam compared to those receiving placebo during the double-blind, R/WD period.

#### Intercurrent events:

The intercurrent events of initiation of additional medications to treat symptoms of TD and requirement of hospitalization for worsening symptoms of TD are included in the definition of Relapse and are considered a Relapse. The intercurrent event of loss to follow-up will be assumed unrelated to treatment and treated in estimation as censored observations. The intercurrent event of death will be handled as follows: if judged unrelated to blinded treatment or TD, death will be treated in estimation as a censored observation; if death is judged as related to blinded treatment or TD then it will be considered a Relapse. Judgement on whether a death is related to blinded treatment will be made prior to data unblinding. Data from subjects who complete or discontinue from the double-blind R/WD period without Relapse will be considered as censored observations.

Population-level summary: The time from Randomization to Relapse between the ecopipam and placebo treatment groups will be tested using a log rank test in the mITT population after having applied the treatment policy strategy specified above.

The primary efficacy analysis approach is in line with the primary estimand. Potential confounders will be identified and sensitivity and/or supplementary analysis may be used to deal with missing data and assess the robustness of conclusions.

# 7.2. Secondary Efficacy Estimand

The secondary endpoint is Time from Randomization (Week 12) to Relapse in all subjects irrespective of age for ecopipam compared to those receiving placebo during the double-blind, R/WD period.

This time-to event endpoint related to Relapse will follow the same treatment policy strategy as the primary efficacy endpoint.

# 8. General Aspects for Statistical Analysis

#### 8.1. General Methods

Study EBS-101-TD-301 is a multicenter global study. Investigative sites in the US are considered conducted under IND 109746 and non-US investigative sites are considered not conducted under IND 109746. Tables, Listings, and Figures will contain combined data from IND and non-IND investigative sites.

All analyses and outputs will be produced using SAS® version 9.4 or later. Unless otherwise specified, efficacy and safety summaries will be presented for each treatment. Continuous variables will be summarized using the number of observations (n), mean, standard deviation (SD), median, minimum, and maximum. Categorical variables will be summarized using number of observations (n), frequency, and percentages of subjects. Time-to-event variables will be summarized using Kaplan-Meier estimates of the 25th percentile, median and 75th percentile.

All relevant subject data will be included in listings. All subjects entered into the database will be included in subject data listings. All by-visit summaries will use the nominal visit. Unscheduled visits will not be summarized but will be included in the listings.

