^c If visits at Weeks 4, 8 and/or 12 are completed in locations other than study clinic due to restrictions because of the COVID-19 pandemic or other qualifying event, then collection of labs for PK assessments are optional.

f Week 2 and 30-Day FU visits will be a telephone call. If there are any abnormal findings, the subject will be brought to the site for full assessment. Subjects who complete the Baseline visit for the EBS-101-TD-391 open label extension study within 30 days of the Week 24 visit are not required to complete the 30-Day FU telephone call.

^g Administration applicable to adult subjects only.

^h Administration applicable to child and adolescent subjects only (6-17 years of age).

ⁱ For women of childbearing potential only. If positive, request a serum HCG on the Chemistry blood sample requisition form for confirmation of pregnancy.

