#### 8.4. Visit Windows

The following visit windows will be used in the summarization or analysis of data. If the subject's last non-missing data point falls within the window, even if additional data points fall within the window, then that last data point will be used. Else, if more than 1 data point falls within a window then the data point closest to the target day will be used. If there are 2 data points equidistant to the target day, one high and one low, then the high data point will be used. Visit windowing will not be applicable to follow-up visits. If a subject terminates the study early, all assessments collected at the Early Termination visit will be assigned to the next scheduled visit (per Schedule of Assessments for the parameter) where the assessment would have been collected.

If Baseline is Day 1, then:

Day 15 (target day = 15) 2 - 21 and no randomization

Week 4 (target day = 29) 22 - 42 and no randomization

Week 8 (target day = 57) 43 - 70 and no randomization

Week 12 (target day = 85) 71 and above with no randomization

Week 13 (target day = 92) 78 - 95 and randomized

Week 14 (target day = 99) 96 - 102 and randomized

Week 15 (target day = 106) 103 - 109 and randomized

Week 16 (target day = 113) 110 - 119 and randomized

Week 18 (target day = 127) 120 - 133 and randomized

Week 20 (target day = 141) 134 - 147 and randomized

Week 22 (target day = 155) 148 - 161 and randomized

Week 24 (target day = 169) 162 and above (randomized and not a follow-up visit)

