#### 12.4. ECG

The following ECG data will be collected at the Screening, Baseline, Weeks 4, 12, 18, and 24 and at the 7-and 14-day Follow Up visits:

- PR interval (msec)
- QRS interval (msec)
- QT interval
- QTc interval (msec)
- Overall ECG result (Normal; Abnormal)

An ECG is optional at unscheduled visits, per the investigator's discretion. All ECGs are monitored, interpreted, reported, and analyzed by a core central facility.

All findings will be presented in the ECG listings.

ECG analysis will consist of:

This document is confidential.

SAP text Version: SAP text 3.0 6-Dec-2023

Controlled Document ID: 3903A.02, Effective Date 31-Aug-2020

- Change from baseline for HR, PR, QRS, and QTcF for each treatment group. (QT and QTcB data will be in listings)
- Shift from baseline in overall ECG result.
- Treatment-emergent morphology findings will be listed.
- Categorical outlier analysis for HR, PR, QRS and QTcF by treatment group.
   The following categorical outliers will be summarized:

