# Adults:

ECG interval	Categorical outlier criteria
QTcF	Treatment-emergent value of > 450 and ≤ 480 ms when not present at baseline (new onset)
	Treatment-emergent value of > 480 and ≤ 500 ms when not present at baseline (new onset)
	Treatment-emergent value of > 500 ms when not present at baseline (new onset)
	Increase of QTcF from baseline of > 30 and ≤ 60 ms
	Increase of QTcF from baseline > 60 ms
PR	Increase of PR from baseline > 25% resulting in PR > 200 ms
QRS	Increase of QRS from baseline > 25% resulting in QRS > 120 ms
HR	Decrease of HR from baseline > 25% resulting in HR < 50 bpm
	Increase of HR from baseline > 25% resulting in HR > 100 bpm

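### SAP 8.1 keeps unscheduled visits out of summaries with no exception for any-time safety analyses, so an ECG outlier or C-SSRS rating seen only at such a visit can be missing from its table

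*SAP*

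**What the plan says.** SAP 8.1 gives two consecutive rules. The first is "All by-visit summaries will use the nominal visit". The second is "Unscheduled visits will not be summarized but will be included in the listings". The second is not worded as applying to by-visit tables only, and no safety analysis is exempted.

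SAP 8.4 then says "The following visit windows will be used in the summarization or analysis of data", and assigns data by study day. The subject's last non-missing value is used if it falls in the window. Otherwise, "if more than 1 data point falls within a window then the data point closest to the target day will be used". Unscheduled data are not excluded there. Follow-up visits are not windowed.

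SAP 12.4 foresees ECGs outside the schedule: "An ECG is optional at unscheduled visits, per the investigator's discretion". It plans a categorical outlier analysis of HR, PR, QRS and QTcF by treatment group and does not say which ECGs feed it. The criteria are any-time criteria. One of them reads: "Treatment-emergent value of > 500 ms when not present at baseline (new onset").

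SAP 12.6 counts subjects with suicidal ideation and behavior at all visits except the 30-day call. It defines no any-time post-baseline row.

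Protocol Table 3, footnote f, adds a trigger for extra on-site assessment after the Week 2 and 30-day calls: "If there are any abnormal findings, the subject will be brought to the site for full assessment".

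**The concern.** Unscheduled assessments are often made because something looks wrong, so they are among the likelier places to find an extreme value. An outlier table exists to report whether any subject crossed a fixed threshold after dosing. If its source data stop at scheduled visits, it answers a narrower question than its criteria imply, and nothing in the table would tell the reader so.

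The ECG schedule leaves room for this. On-treatment ECGs are planned at Weeks 4, 12, 18 and 24. None is planned between Weeks 4 and 12, when open-label subjects are at their full assigned dose. Safety and tolerability are a secondary objective (SAP 3.2), and a zero in the top QTcF category is a line that gets quoted.

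**Working it through.** The plan states no figure for this point, so the check is mainly a reading of the sections against each other.

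1. **ECG outliers under SAP 8.1.** Take a subject whose scheduled ECGs are all normal and whose only QTcF above 500 ms is on an unscheduled ECG. The subject meets the SAP 12.4 criterion. SAP 8.1 bars the visit from summaries, and nothing in 12.4 overrides that. The subject is listed but not counted.

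2. **The same data under SAP 8.4.** The Week 4 window is days 22 to 42, with target day 29. Suppose a normal scheduled ECG on day 29, an outlier on an unscheduled ECG on day 33, and later ECGs at scheduled visits. The distances from target are 0 and |33 − 29| = 4 days, so the normal value is kept and the outlier is dropped. Now put the unscheduled ECG on day 50. It falls in the Week 8 window (days 43 to 70), where no ECG is scheduled. It is the only value there, so 8.4 would keep it and 8.1 would not. The two sections can therefore give different tables. Neither selects the worst value.

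3. **C-SSRS.** Protocol 12.1.1 uses the Since Last Visit version at every visit after Screening. If a rating is taken at an unscheduled visit, and that visit counts as the last one, the next scheduled rating asks only about the time since then. Ideation recorded at the unscheduled visit may not be asked about again. Under 8.1 the rating that did record it is not summarized.

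4. **The adverse event route.** Under Protocol 12.2.1 an abnormal test is an AE only if it causes signs or symptoms, needs intervention, interrupts or stops drug, or is judged clinically significant by the investigator. The AE, SAE and AESI tables are built from events, so SAP 8.1 does not remove anything from them. A threshold crossing without symptoms or action, and judged not significant, reaches neither the AE table nor, under 8.1, the outlier table.

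5. **Tables that are not damaged.** The laboratory and HbA1c shifts (SAP 12.2) and the weight shifts (SAP 12.3) are all specified by visit. No any-time table exists there for the sentence to affect.

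6. **Size.** The planned number treated is 196 + 40 = 236. These figures show only what one case does to a rare-event table:
   - No cases in 236: upper 95% bound 1 − 0.05^(1/236) = 1.26%.
   - One case in 236: 1/236 = 0.42%, exact 95% CI 0.01% to 2.34%.

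   For a range, assume a true any-time outlier incidence p of 2% to 5%, and let s be the share of outlier subjects found only on unscheduled ECGs. Both are assumptions. The expected count is 236 × p × (1 − s):

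| s | p = 2% | p = 5% |
|---|---|---|
| 0 | 4.7 | 11.8 |
| 10% | 4.2 | 10.6 |
| 25% | 3.5 | 8.9 |
| 50% | 2.4 | 5.9 |

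With s = 0 nothing is lost.

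**The case against.** The best defense is context. The sentence comes directly after one about by-visit summaries, and the pair can be read as a rule for by-visit tables only. On that reading the outlier counts are untouched. The reading is possible, but the text does not say so and 12.4 does not name its source ECGs, so the ambiguity remains.

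Second, there are backstops. Clinically significant abnormalities are AEs. Values that are SAEs or lead to stopping drug must be recorded as AEs (Protocol 12.4). Suicidal ideation and behavior has its own AESI table (SAP 12.1). A new positive answer on C-SSRS question 4 or 5 leads to discontinuation (Protocol 7.5), and SAP 8.4 carries Early Termination assessments into the next scheduled visit. SAP 12.6 also refers to all visits, which could be read to include unscheduled ones. This largely covers the most serious cases. It does not cover an ECG value judged not significant, and Protocol 7.5 attaches no discontinuation rule to positive answers on the other C-SSRS ideation questions.

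Third, footnote f does not call the on-site assessment unscheduled, and its coding is not stated. After a Week 2 call it could fall in the Day 15 window (days 2 to 21). That is a fair point, and it is another reason to reconcile 8.1 with 8.4.

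A reader might infer something stronger: that no unscheduled finding reaches any table, that the laboratory, HbA1c and weight tables are compromised too, and that safety signals as a whole are under-counted. The documents do not support this. AE-based tables and listings are unaffected, 8.4 could admit some unscheduled values, and limiting by-visit shift tables to scheduled visits is ordinary practice. A worst-value laboratory table would be a new analysis, not the repair of a contradiction.

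**Conclusion.** The point holds in a narrow form. Followed as written, SAP 8.1 can give a wrong count in the ECG categorical outlier table and can leave a C-SSRS rating out of its summary. Neither the 8.4 windows nor the AE route fully repairs this. The C-SSRS limb is the weaker of the two: it depends on how sites treat the look-back after an unscheduled rating, and the AESI table partly covers it.

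The size cannot be derived. The documents give neither the number of unscheduled assessments nor any rate of outliers found only there, so the loss may be zero. The table of expected counts rests wholly on assumed incidences and shares. What can be said is that in a rare-event table one omitted subject separates none from some. This is a cheap clarification worth making, not evidence that signals have been missed.

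**What to change.** - **SAP 8.1:** limit the sentence to by-visit descriptive statistics, and reconcile the nominal-visit rule with the 8.4 windows so that one rule assigns each value to a visit.
- **SAP 12.4:** state that categorical ECG outliers use all post-dose ECGs, scheduled or unscheduled, assigned to study period by date.
- **SAP 12.6:** add an any-time post-baseline row for ideation and for behavior that includes unscheduled ratings.

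The by-visit laboratory, HbA1c and weight shift tables can stay on scheduled visits.

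The cost is a few sentences of SAP text and a little more programming: an any-time outlier flag, period assignment by date and the extra C-SSRS row. No new data are needed. The outlier counts may come out slightly less favorable. The change should be made before unblinding.
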